#### **4.3 General Guidelines for Other Investigative Sites**

N/A

#### **4.4 Registration Process for Other Investigative Sites**

N/A

### **5. TREATMENT PLAN**

#### **5.1 Treatment Regimen**

The investigational therapy used in the course of this study is BKM120. Treatment with BKM120 starts 2 weeks prior to cisplatin and radiotherapy and continues until the end of radiotherapy.

Study medication will be self-administered by the patients continuously throughout radiation. In order to assure compliance with protocol procedures drug administration will be thoroughly explained to the patients. During the study, BKM120 will be administered orally. It is given every day including weekend days. Administration of BKM120 stops with the end of radiotherapy. If radiation is held due to toxicity, BKM120 and cisplatin will be held as well. If cisplatin is held due to toxicity, BKM120 and radiation will continue. If BKM120 is held due to toxicity, cisplatin and radiation will continue. Medication labels will comply with US legal requirements and be printed in English. The storage conditions for study drug will be described on the medication label.

BKM120 will be provided by Novartis Pharmaceuticals free of charge. BKM120 is formulated as capsules for oral administration of 10mg and 50mg strength. Capsules are packaged in bottles. BKM120 capsule cannot be crushed and has to be swallowed. It cannot be given via enteral feeding tube.

If vomiting occurs, no attempt should be made to replace the vomited dose.

#### **5.2 Treatment Assignment**

This is a non-randomized study, no treatment assignment is necessary. Patients will be enrolled in cohorts of 3- 6 per dose level. Once the MTD is reached, an additional 10 patients will be treated at that dose level and an amendment will be submitted to OHRS to declare the dose.

#### **5.3 Dose Escalation and Stopping Rules**

The dose-limiting toxicity (DLT), as defined in Section 5.5, will be the basis for determining the maximum tolerated dose (MTD). Any subject who receives at least one dose of the study drug (BKM120) will be included in analysis for DLT. Treatment cohorts will be dosed in escalating order, as outlined in Table 8, only after the safety of the previous dose level has been established, or until an MTD has been determined.

Subsequent dose levels will be opened for treatment as follows:

1) Escalation to the subsequent dose level will occur only after all subjects in the previous cohort have completed the full 7-week course of BKM120-CRT and have been evaluated for safety and toxicity. Safety will be evaluated based on the incidence of adverse events (AEs), physical exam findings, and clinical laboratory test results. A review of the safety data for each cohort will be conducted when all of the above data are available. In the event that an MTD is not reached after dose level 5, the study will be considered to have reached a biologically acceptable dose appropriate for Phase II study. Any further dose escalations or de-escalations will require a protocol amendment.

2) Three patients will initially be enrolled at dose level 1. The following rules apply for the advancement to the next dose level and to determine the MTD (see also Table 7). Enrollment may proceed at the higher dose according to the rules after three patients have been treated for the 2 weeks of BKM120 followed by 7 weeks of BKM120+CRT at a given dose level and safety data have been reviewed. The dose will be increased until a DLT is observed in one subject. Dose limiting toxicity is graded according to the National Cancer Institute’s CTCAE v4.0 (<http://ctep.cancer.gov/forms/CTCAEv4.pdf>).

Once a DLT occurs, additional subjects will be added to the cohort until either a second subject experiences a DLT or six subjects are treated at that dose level. If no additional subject experiences a DLT at the trigger dose-level, further dose escalation as outlined in Table 8 will be explored in cohorts of three subjects.

If two or more subjects experience a DLT at a given dose, then three additional subjects will be treated at the next lower dose, unless six subjects have already been treated at that dose.

The maximum tolerated dose is the highest dose studied for which the incidence of DLT is less than 33%. The final cohort of three to six subjects may be expanded to 10 subjects to provide additional safety and pharmacokinetic data.

The decision to enroll subjects in the next higher dose level will be made at the discretion of the principal investigator.

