**Table 7: Dose Escalation Criteria**

Number of Subjects per Cohort with DLT During Treatment Period	Dose Escalation Decision
0 out of 3	Enter 3 subjects at the next dose level.
1 out of 3	Enter 3 more subjects at this dose level.  If no additional DLT, proceed to the next dose level.  If an additional DLT occurs (i.e. $\geq$ 2 DLTs/6 subjects), dose

	escalation is stopped and the previous dose level is declared the MTD.
≥ 2	The previous dose level is declared MTD. There is no advancement to higher dose levels.

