#### **5.5 Dose-Limiting Toxicity**

Toxicity will be assessed using the NCI Common Toxicity Criteria for Adverse Events, version 4.0

[http://evs.nci.nih.gov/ftp1/CTCAE/CTCAE\\_4.03\\_2010-06-14\\_QuickReference\\_8.5x11.pdf](http://evs.nci.nih.gov/ftp1/CTCAE/CTCAE_4.03_2010-06-14_QuickReference_8.5x11.pdf) unless

otherwise specified (e.g., hyperglycemia). A dose-limiting toxicity (DLT) is defined as an adverse event or abnormal laboratory value assessed as unrelated to disease, disease progression, inter-current illness, or concomitant medications, and occurs < 28 days following the last dose of BKM120, and meets any of the criteria listed in Table 9.

Whenever a patient experiences toxicity that fulfills the criteria for a DLT (or a potential DLT), treatment with BKM120 will be interrupted (if not otherwise specified) and the toxicity will be followed up as described in section 5.3. Exceptions are CTCAE grade 2 hyperglycemia and CTCAE grade 2 mood alteration, where BKM120 treatment will be continued under appropriate co-medication. The criteria for dose-limiting toxicities are outlined in Table 9.

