### **5.14 Criteria for Removal from Study Treatment and/or Study Itself**

For patients who are unable to tolerate the protocol-specified dosing schedule, dose adjustments are permitted in order to keep the patient on study drug. If administration of BKM120 must be interrupted because of unacceptable toxicity, drug dosing will be interrupted or modified according to rules described in Table 11. Toxicity will be assessed using the NIH-NCI Common Terminology Criteria for Adverse Events, version 4.0.

[http://evs.nci.nih.gov/ftp1/CTCAE/CTCAE\\_4.03\\_2010-06-14\\_QuickReference\\_8.5x11.pdf](http://evs.nci.nih.gov/ftp1/CTCAE/CTCAE_4.03_2010-06-14_QuickReference_8.5x11.pdf)

The reason for study treatment discontinuation and/or study removal and the date the participant was removed must be documented in the case report form (CRF). Alternative care options will be discussed with the participant.

Reasons that a patient may discontinue study treatment and/or discontinue participation in a clinical study are considered to constitute one of the following:

1. adverse event(s)
2. abnormal laboratory value(s)
3. abnormal test procedure result(s)

4. disease progression
5. protocol violation
6. subject withdrew consent
7. lost to follow-up
8. administrative problems
9. death

A QACT Treatment Ended/Off Study Form should be filled out when a participant completes study treatment and again when the participant comes off study. This form can be found on the QACT website or obtained from the QACT registration staff.

In the event of unusual or life-threatening complications, investigators must immediately notify the Overall PI, [name] at [contact] or page at [contact].

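### The one-dose rule in section 5.3 counts early leavers as DLT-free although they never received the cisplatin step under test, and it conflicts with the completion rules beside it

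*Combined protocol and SAP*

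**What the plan says.** Section 5.3 states who enters the DLT count: "Any subject who receives at least one dose of the study drug (BKM120) will be included in analysis for DLT". That sentence does not mention cisplatin or radiation. Section 5.1 describes the lead-in: "Treatment with BKM120 starts 2 weeks prior to cisplatin and radiotherapy and continues until the end of radiotherapy". Table 8 holds BKM120 at 40 mg for levels 1, 2 and 3 and raises weekly cisplatin from 30 to 35 to 40 mg/m². Under section 5.5 a DLT must be an event that "occurs < 28 days following the last dose of BKM120", so the window is tied to each patient's own last dose. Section 5.14 lists reasons for leaving that need have nothing to do with toxicity, among them "subject withdrew consent".

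Two other sentences in section 5.3 control escalation. Rule 1: "Escalation to the subsequent dose level will occur only after all subjects in the previous cohort have completed the full 7-week course of BKM120-CRT". Rule 2 allows enrollment at the higher dose "after three patients have been treated for the 2 weeks of BKM120 followed by 7 weeks of BKM120+CRT at a given dose level", once safety data have been reviewed. In Table 7, 0 of 3 leads to "Enter 3 subjects at the next dose level", 1 of 3 adds three patients, and 2 or more stops escalation. The MTD is set by an observed rate, in per cent: "The maximum tolerated dose is the highest dose studied for which the incidence of DLT is less than 33".

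The document gives no DLT-evaluable set, no minimum cisplatin exposure and no replacement rule. Section 4.1 deals only with registered patients who never receive therapy.

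**The concern.** The primary endpoint is the MTD, and a 3+3 design reaches it by counting patients without a DLT. The count is informative only if those patients received the dose being judged. At levels 2 and 3 the only new element is more cisplatin. A patient who withdraws on day 10 of the lead-in has received none, yet the one-dose rule enters that patient as DLT-free.

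Two things are at stake. The next cohort could be dosed higher on two informative patients instead of three. The DLT incidence that defines the MTD could also be diluted. Separately, section 5.3 gives no single answer on what to do when a patient stops early without a DLT.

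**Working it through.** **Inputs.** The escalation rule is from Table 7, the stated escalation probabilities from section 13, and the dose steps from Table 8. Let p be the true DLT rate of the full regimen and q = 1 − p.

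**Step 1: reproduce section 13.** A level is passed with 0 of 3, or with 1 of 3 followed by 0 of 3:

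P(escalate) = q³ + 3pq² × q³.

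At p = 0.4: 0.216 + 0.432 × 0.216 = 0.309, matching the stated 0.31. All five stated values reproduce (table below).

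**Step 2: one of the first three is unexposed, DLT-free, counted and not replaced.** Two patients then carry the information, and three exposed patients are added if one of the two has a DLT:

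P(escalate) = q² + 2pq × q³.

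At p = 0.4: 0.36 + 0.48 × 0.216 = 0.464.

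| True DLT rate | Section 13 | Step 1 | Step 2 | Difference |
|---|---|---|---|---|
| 20% | 0.71 | 0.709 | 0.804 | 0.095 |
| 30% | 0.49 | 0.494 | 0.634 | 0.140 |
| 40% | 0.31 | 0.309 | 0.464 | 0.154 |
| 50% | 0.17 | 0.172 | 0.312 | 0.141 |
| 60% | 0.08 | 0.082 | 0.191 | 0.108 |

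Step 2 is conditional on one such patient, and it applies only if rules 1 and 2 are not strictly enforced.

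**Step 3: put the three rules side by side.** Suppose one of three level 2 patients withdraws on day 10 and the other two finish without a DLT.

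- One-dose rule with Table 7: 0 of 3, so escalate.
- Rule 1: not all subjects completed, so no escalation. The withdrawn patient can never complete, and no way forward is given.
- Rule 2: only two patients have had the 9 weeks, so a fourth is needed. Without a further DLT, the one-dose count is then 0 of 4, which Table 7 does not list.

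**Step 4: can rule 1 be applied literally?** Not always. Table 7 escalates after 1 DLT in 6, but some DLTs end BKM120 for that patient (confirmed grade 4 hyperglycemia and grade 4 fatigue in Table 11). That patient does not complete BKM120-CRT, so a literal rule 1 would block an escalation that Table 7 directs. The team has to interpret completion, and section 5.3 leaves the decision to the principal investigator's discretion.

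**Step 5: the MTD denominator.** Two DLTs in six exposed patients is 2/6 = 33.3%, which is not below 33%. Add one unexposed patient under the one-dose rule and it is 2/7 = 28.6%, which is below 33%, although Table 7 says to stop at two. Rules 1 and 2 govern when the next level opens; they do not govern this denominator.

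**Step 6: cisplatin content of a completed course.** No number of cisplatin doses is attached to completion. The Table 9 notes make more than 7 BKM120 doses missed for an adverse event a DLT; nothing similar exists for cisplatin.

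**The case against.** The strongest answer is that rules 1 and 2 already provide the safeguard. The one-dose sentence says who is analyzed, which ensures that early DLTs count. It does not open the next level. Section 5.2 allows cohorts of three to six, so enrolling a fourth patient and reading 0 DLTs among three completers is workable. Further checks are the safety review before escalation, the review of adverse events of grade 2 or higher, and the monitoring committee (section 12.2). Section 5.8.2 also lets weekly cisplatin be added if treatment was held.

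Much of this stands. A reader might infer that levels 2 and 3 could clear on patients who never received cisplatin. The documents do not support that: rule 2 needs three patients treated through BKM120+CRT, so a wholly unexposed cohort cannot clear a level. A reader might also take the step 2 figures as the plan's true operating characteristics. They are not, because they need the completion rules to be relaxed.

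Three further limits apply. Cisplatin cut, held or stopped for toxicity under section 6.1 is outside the point, because those patients were exposed. At levels 4 to 6 the rising drug is BKM120, which section 2.2.8.8 expects to reach steady state after 1 week, so a late lead-in leaver there has had some exposure to the step. And 46 (6 × 6 + 10) is an estimated maximum, so it is too strong to say that it leaves no room for replacements. Clearing a level with exactly six patients has probability 3pq⁵, at most 0.20 (at p = 1/6), so the full 36 escalation places will rarely be used.

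The objection does not remove the conflict between the three rules, the missing cisplatin minimum, or the uncorrected MTD denominator.

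**Conclusion.** The point holds in this form: a stated rule, not merely an omission, lets a patient who never received the cisplatin step count as DLT-free, and the completion rules beside it limit the damage without resolving it. Applied literally, rule 1 stalls the level after one early withdrawal. Rule 2 implies a fourth patient for whom Table 7 has no row. Neither sets a cisplatin minimum or corrects the MTD incidence.

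If the completion rules are relaxed and one of the first three patients is an unexposed leaver without a DLT, the chance of escalating rises by 0.10 to 0.15 across true DLT rates of 20% to 60%; the largest rise is from 0.31 to 0.46 at 40%. If they are enforced, the cost is a stalled or improvised cohort decision rather than a biased one. The documents do not give the frequency of such patients, so no unconditional size can be stated. The change should be made because the primary endpoint rests on this count and the remedy is cheap.

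**What to change.** Replace the one-dose sentence in section 5.3 with wording such as:

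> Every subject given any BKM120 enters the safety analysis, and any DLT counts. For Table 7 and the MTD, a subject without a DLT counts only if he or she started CRT and received at least a pre-set share of planned cisplatin and of planned BKM120, unless the shortfall was a change for toxicity under section 6. Any other subject without a DLT is replaced at the same level.

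The trial team should set the shares. An example is 5 of 7 cisplatin doses and 75% of BKM120 doses. The cisplatin minimum should be a share of the planned dose. It should not be justified by the cumulative 200 mg/m² cited in section 2.3: five doses give 200 mg/m² only at 40 mg/m² (5 × 35 = 175; 5 × 30 = 150), and that figure is a cut-off for successful treatment, not for tolerability.

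Word rules 1 and 2 in terms of DLT-evaluable subjects. State in section 13 that 46 means DLT-evaluable patients in escalation plus the 10 expansion patients, with replacements additional. The Table 9 criteria do not change, and the section 13 probabilities then apply as stated.

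Cost: if all 36 escalation places were used, an assumed non-toxicity loss d of 5%, 10% or 20% means 36/(1 − d) − 36 = 1.9, 4.0 or 9.0 replacements, and usually fewer. A cohort that needs a replacement may wait up to about 9 weeks longer.

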### 3. PARTICIPANT SELECTION

Depending on toxicities encountered during the trial. Up to 46 patients are anticipated to be treated on this protocol.

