**Table 8: Dose Escalation**

Dose level	BKM120 (mg, daily)	Cisplatin (mg/m  , weekly)
-1	20	30
1	40	30
2	40	35
3	40	40
4	60	40
5	80	40
6	100	40

BKM120 will start **2 weeks** prior to first dose of cisplatin and radiation start.

Patients will be assessed weekly for adverse events for the duration of the treatment (2 weeks of BKM120 and 7 weeks of BKM120+CRT = 9 weeks) and every 2 weeks after conclusion of CRT during the first month, then monthly for 3 months, then every 3 months until first progression, death, or 2 years post study entry whichever occurs first.

After establishment of MTD, 10 additional patients will be enrolled at the MTD dose level to gain additional experience with this regimen and dose. If the MTD is not reached, because ≤ 1 DLT is encountered at dose level 6, ten additional patients will be enrolled at this dose level. If there are greater than 2 DLTs at dose level 1, enrollment will continue at dose level -1 with no advancement beyond dose level -1.

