## 13. STATISTICAL CONSIDERATIONS

This trial follows a standard 3+3 phase I design. The primary endpoint is to determine the MTD. Patients will be started at a given dose and escalated according to the information outlined in section 5.3. The table below gives the probabilities of the dose escalation scheme outlined in section 5.3.

True Rate of DLT	Probability of Escalation
20%	.71
30%	.49
40%	.31
50%	.17
60%	.08

For example, if the true rate of DLT is 20% at a given dose, there is a 71% probability of escalating to a higher dose.

At most, 46 patients are estimated to be accrued. This is based on studying 6 levels of BKM120+Cisplatin (section 5.3) with at most 6 patients per level plus an additional 10 at the MTD (these 10 accrued to ensure that the adverse event rate at the MTD is acceptable). The estimation of adverse events will be based on studying these 10 additional patients. The width of the 90% confidence interval for the estimation of the adverse event rate will be no more than 56%. The monthly accrual rate is estimated to be 2 to 3 patients.

For secondary objectives: best overall response rate will be summarized as a proportion with a corresponding 90% exact confidence interval, the distributions of progression and survival will be estimated using a Kaplan-Meier method with corresponding 90% confidence intervals for the median or time-specific event time, scores from the GAD-7 and the PHQ-9 to assess mood will be summarized across the timepoints of assessment. Several correlative studies are planned to learn more about how BKM120 blocks PIK. NexGen sequencing of the specimens and studies to investigate the influence of the NFE2L2/KEAP1/CUL3 are planned (see sections 9.1 and Appendix D). Given the small sample size of this trial, these studies are exploratory.

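### Section 5.3 ends escalation after dose level 5 (80 mg), while Table 8, the expansion rule and the sample size all run to level 6 (100 mg)

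*Combined protocol and SAP*

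**What the plan says.** Section 5.3, item 1 gives a rule for the case where escalation finds no MTD: "In the event that an MTD is not reached after dose level 5, the study will be considered to have reached a biologically acceptable dose". The sentence goes on to call that dose suitable for Phase II, and the next one adds: "Any further dose escalations or de-escalations will require a protocol amendment".

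Other current text sets a different ceiling.

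- **Table 8**, which section 5.3 names as the escalation order, lists level 5 as BKM120 80 mg daily with cisplatin 40 mg/m² weekly. It then lists level 6 as 100 mg with the same cisplatin dose.
- **Table 7** says, for 0 of 3 with DLT: "Enter 3 subjects at the next dose level". After 1 of 3, three more patients are added, and with no further DLT the trial moves up.
- **The text under Table 8** covers an MTD that is not reached because no more than one "DLT is encountered at dose level 6, ten additional patients will be enrolled at this dose level".
- **Section 13** explains the maximum accrual: "This is based on studying 6 levels of BKM120+Cisplatin (section 5.3) with at most 6 patients per level", plus ten at the MTD. Section 3 repeats the total: "Up to 46 patients are anticipated to be treated on this protocol".

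**The concern.** When level 5 clears, the protocol gives two incompatible instructions. Section 5.3, item 1 says the trial has its Phase II dose and may not go higher without an amendment. Table 7, Table 8 and the text under Table 8 say to enter three patients at level 6.

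The MTD is the only primary objective (section 1.2), and this sentence decides what is declared if none is found. The disputed step is from 80 to 100 mg, an increase of 25% (100/80 = 1.25). Section 2.2.8.2 gives 100 mg as the single-agent MTD; here it would be added to cisplatin and radiation. If the level 5 rule is followed, a planned level is never tested and the expansion runs at 80 mg. If the level 6 rule is followed, 3 to 6 patients, or 13 to 16 with the ten-patient expansion, are treated at a dose that item 1 says first needs an amendment.

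**Working it through.** **Inputs.** Six numbered levels from 1 to 6 (Table 8); at most 6 patients per level, ten at the MTD and a maximum of 46 (section 13); the 3+3 rule (Table 7); and the escalation probabilities in section 13.

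**1. Sample size.** Maximum N = levels × 6 + 10.

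- Six levels: 6 × 6 + 10 = 46, which reproduces the stated figure.
- Five levels: 5 × 6 + 10 = 40, which does not.

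The stated maximum therefore assumes that level 6 is open.

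**2. Chance of clearing one level.** With true DLT rate p, c(p) = (1−p)³ + 3p(1−p)² × (1−p)³.

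| p | c(p) | Section 13 |
|---|---|---|
| 20% | 0.709 | .71 |
| 30% | 0.494 | .49 |
| 40% | 0.309 | .31 |
| 50% | 0.172 | .17 |
| 60% | 0.082 | .08 |

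The plan's table is reproduced, so the properties of each level are not in question. At p = 10%, c = 0.906.

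**3. The instructions once level 5 clears (0/3 or 1/6).**

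| Source | Instruction | Top dose |
|---|---|---|
| Section 5.3, item 1 | Declare a Phase II dose; amend to go higher | 80 mg |
| Tables 7 and 8 | Enter three patients at level 6 | 100 mg |
| Text under Table 8 | If at most one DLT at level 6, add ten there | 100 mg |
| Section 13 | Six levels, N = 46 | 100 mg |

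**4. How often this would matter.** The documents give no DLT rates for this combination, so a constant rate at every level is assumed for illustration. The conflict arises if levels 1 to 5 all clear, with probability c⁵. If level 6 also clears, with overall probability c⁶, the rules end at 80 and 100 mg for that reason.

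| Assumed rate | c⁵ (conflict arises) | c⁶ (levels 1 to 6 all clear) |
|---|---|---|
| 10% | 0.61 | 0.55 |
| 20% | 0.18 | 0.13 |
| 30% | 0.03 | 0.015 |

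With rates that rise over levels 1 to 5, the chance that the conflict arises is 46% for 5, 10, 10, 15, 20% and 7% for 15, 20, 25, 30, 35%.

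**The case against.** The best defence is that one stale number is outvoted by everything else. Table 8, the level 6 expansion rule, the six levels in section 13 and the total of 46 all agree. The amendment sentence also speaks of further de-escalations although level −1 is already planned, so *further* may simply mean outside Table 8. This stands as evidence of intent: level 6 was probably meant. It does not make the text consistent, because the amendment sentence directly follows the level 5 sentence. The principal investigator's discretion over opening the next level cannot waive an amendment that the protocol requires.

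A second defence is that level 5 meant the fifth BKM120 dose, which is 100 mg in the section 6 reduction schedule. That schedule uses letters A to E. Section 5.3 uses numbered levels and points to Table 8, where level 5 is 80 mg.

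Two stronger readings are tempting, and the documents do not support either.

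- A reader might infer that stopping at level 5 would leave the Phase II dose resting on 3 to 6 patients. Section 5.3 defines the MTD as the highest dose studied with a DLT incidence below 33%. A cleared level 5 that was the highest dose studied would meet this (0/3 = 0%; 1/6 = 16.7%). Section 5.2 then applies: "Once the MTD is reached, an additional 10 patients will be treated at that dose level". The schema note and section 13 point the same way. One sentence in section 5.3 is looser, "The final cohort of three to six subjects may be expanded to 10 subjects to provide additional safety and pharmacokinetic data", but permissive wording does not cancel the expansion.
- A reader might take the 71% to 8% in section 13 as the chance that the two rules end at different doses. Those figures describe clearing a single level, so for level 6 they apply only after levels 1 to 5 have cleared. They also miss a second route. If level 6 fails, item 2 sends three more patients to level 5 unless six were already treated there. Two or more DLTs among those three would make at least 2/6, which is not below 33%, and the final dose would fall below 80 mg. With 30% at both levels, and given that level 5 has cleared, this route adds 0.694 (level 5 cleared as 0/3) × 0.506 (level 6 fails) × 0.216 (two or more of three) = 0.076. The conditional chance rises from 49% to about 57%. Table 7 does not mention this step, so it counts only under the item 2 text.

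**Conclusion.** The level 5 threshold in section 5.3, item 1 is wrong as written. It contradicts Table 8, the expansion rule beneath it and the basis of the 46 patients, and nothing in the current text reconciles them. What is left unsettled is the highest dose allowed without an amendment and the dose for the expansion when no MTD is found: 80 or 100 mg.

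The severity is minor. The 3+3 rule at each level is unaffected, and the maximum of 46 is correct if level 6 is intended. The probabilities in the working rest on assumed DLT rates and on independence between patients; if the early levels are already toxic, the conflict is unlikely to arise. The c⁶ figures count only the case where level 6 clears, so they do not cover every way in which the final doses could differ.

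**What to change.** In section 5.3, item 1, change *dose level 5* to *dose level 6*. Replace the next sentence with: *Escalation above dose level 6 or de-escalation below dose level −1 will require a protocol amendment.* Table 8, the expansion rule and the 46 patients stay as they are.

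The cost is two sentences, but the change is not neutral. It removes the amendment step that the present text places between 80 and 100 mg, so the sponsor must confirm that level 6 is intended. The safety review of the previous cohort and the principal investigator's decision would still come before level 6 opens.

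If level 5 is the intended ceiling, leave item 1 and make these changes instead:

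- delete level 6 from Table 8;
- change *dose level 6* to *dose level 5* in the text beneath it;
- change six levels to five in section 13;
- change 46 to 40 in sections 3 and 13.
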